10.2.4 Severity of Adverse Events

The severity of an event describes the degree of impact upon the subject and/or the need for medical care necessary to treat the event. AEs reported for subjects participating in this study will be graded using the NCI CTCAE v4.03 (Table 10-1).

The Investigator will grade the severity of each AE using, when applicable, the NCI CTCAE v4.03. For AEs not included in the NCI CTCAE v4.03, the criteria outlined in Table 10-1 should be used as a general guideline.

Table 10-1 Grading for Adverse Events Not Covered in the NCI CTCAE

Severity	Description
Grade 1 – Mild	Asymptomatic or mild symptoms; clinical or diagnostic observations only; intervention not indicated
Grade 2 – Moderate	Minimal, local or noninvasive intervention indicated; limited age-appropriate instrumental activities of daily living (ADL)
Grade 3 – Severe	Medically significant but not immediately life threatening; hospitalization or prolongation of hospitalization indicated; disabling; limiting self-care ADL.
Grade 4 – Life-threatening	Life-threatening consequences; urgent intervention indicated
Grade 5 – Fatal	Death

ADL = activities of daily living; NCI CTCAE = National Cancer Institute-Common Terminology Criteria for Adverse Events

10.2.5 Relationship to Study Drug

The relationship of an AE to the investigational product should be determined by the Investigator according to the following definitions:

- **Not Related:** Evidence exists that the AE has an etiology other than the study drug (such as a preexisting condition, underlying disease, intercurrent illness, or concomitant medication); and/ or the temporal relationship of the AE/SAE to the investigational product administration makes the relationship unlikely.
- **Possibly/Probably Related:** A temporal relationship exists between the event onset and administration of the study drug; and it cannot be readily explained by the subject’s clinical state or concomitant therapies; and it may appear with some degree of certainty to be related based on the known therapeutic and pharmacologic actions of the drug. Additional criteria to consider include in the case of cessation or reduction of the dose,

the event abates or resolves and reappears upon re-challenge. It should be emphasized that ineffective treatment should not be considered as causally related in the context of AE reporting.

These criteria, in addition to good clinical judgment, should be used as a guide for determining the causal assessment. If it is felt that the event is not related to study drug therapy, then an alternative explanation should be provided.

10.2.6 *Unexpected Adverse Events*

An adverse reaction is ‘unexpected’ if its nature and severity are not consistent with the information contained within the current GBT440 IB.

10.3 **Reporting Adverse Events**

Reporting of AEs prior to dosing should only include SAEs resulting from any protocol-related interventions.

10.3.1 *Diagnosis versus Signs and Symptoms*

If known, a diagnosis should be recorded on the eCRF rather than individual signs and symptoms (e.g., record only liver failure or hepatitis rather than jaundice, asterixis, and elevated transaminases). However, if a constellation of signs and/or symptoms cannot be medically characterized as a single diagnosis or syndrome at the time of reporting, each individual event should be recorded as an AE or SAE on the eCRF. If a diagnosis is subsequently established, all previously reported AEs based on signs and symptoms should be nullified and replaced by one AE report based on the single diagnosis, with a starting date that corresponds to the starting date of the first symptom or sign of the eventual diagnosis.

10.3.2 *Adverse Events Occurring Secondary to Other Events*

In general, AEs occurring secondary to other events (e.g., cascade of events or clinical sequelae) should be identified by their primary cause. For example, if severe diarrhea is known to have resulted in dehydration, it is sufficient to record only diarrhea as an AE or SAE on the eCRF.

However, medically significant AEs occurring secondary to an initiating event that are separated in time should be recorded as independent events on the eCRF. For example, if a severe gastrointestinal hemorrhage leads to renal failure, both events should be recorded separately on the eCRF.

10.3.3 *Persistent or Recurrent Adverse Events*

A persistent AE is one that extends continuously, without resolution between subject evaluation time points. Such events should only be recorded once in the eCRF unless the severity changes (increases or decreases). If a persistent AE becomes more or less severe, the AE should be recorded as separate AEs for each Grade of severity.

If the event becomes serious, it should be reported to the Sponsor or the Sponsor's designated CRO's Drug Safety Department within 24 hours of the Investigator, designee, or site personnel's knowledge of the event. The AE eCRF should be updated to add the SAE, providing the date that the event became serious. The updated eCRF should include both the non-serious and serious designated AEs.

A recurrent AE is one that resolves between subject evaluation time points and subsequently recurs. All recurrent AEs should be recorded separately on an Adverse Event eCRF.

10.3.4 *Abnormal Laboratory Values*

Only clinically significant laboratory abnormalities will be recorded as AEs or SAEs on the eCRF (e.g., abnormalities that require study drug dose modification, discontinuation of study drug, more frequent follow-up assessments, further diagnostic investigation).

If the clinically significant laboratory abnormality is a sign of a disease or syndrome (e.g., increased alkaline phosphatase and bilirubin associated with cholecystitis), only the diagnosis (e.g., cholecystitis) needs to be recorded on the eCRF.

If the clinically significant laboratory abnormality is not a sign of a disease or syndrome, the abnormality itself should be recorded as an AE or SAE on the eCRF. If the laboratory abnormality can be characterized by a precise clinical term, the clinical term should be recorded as the AE or SAE. For example, an elevated serum potassium level of 7.0 mEq/L should be recorded as "hyperkalemia."

Observations of the same clinically significant laboratory abnormality from visit to visit should not be repeatedly recorded as AEs or SAEs on the Adverse Event eCRF, unless their severity increases or decreases, or the seriousness or etiology changes.

10.3.5 *Reporting Serious Adverse Events (SAEs)*

All SAEs and AESIs, regardless of causal attribution, that occur in this study will be reported to the Sponsor's designated CRO's Drug Safety Department within 24 hours of the Investigator, designee, or site personnel's knowledge of the event. The SAE/AESI will be reported by completing the SAE/AESI eCRF in the EDC system.

In the event that the EDC system is not available, a paper SAE/AESI report form must be submitted to the CRO's Drug Safety Department ([contact] or faxed to [name]) within 24 hours of becoming aware of the event. The Principal Investigator or designee must complete the SAE/AESI eCRF page as soon as the EDC system becomes available.

Follow-up reports must be submitted in a timely fashion as additional information becomes available. The Sponsor or designee may request additional source documentation pertaining to the SAE/AESI from the investigational site. If a subject is permanently withdrawn from the study due to a SAE, this information must be included in the initial or follow-up SAE report in the eCRF.

The Investigator is responsible for notifying the Institutional Review Board (IRB) or Independent Ethics Committees (IEC) of SAEs, in accordance with local regulations. The Sponsor or designee is responsible for reporting SAEs to the relevant regulatory authorities, and participating Investigators, in accordance with ICH guidelines, FDA regulations, and/or local regulatory requirements.

Properly anonymized and de-identified documents (e.g., hospital discharge summaries, autopsy reports, and/or death certificates) as available will be provided to the CRO's Drug Safety Department for all reported SAEs/AESIs.

10.3.6 Suspected Unexpected Serious Adverse Reaction (SUSAR) Reporting

An SAE may qualify for mandatory expedited reporting to regulatory authorities if the SAE is attributable to the study drug and is not listed in the current IB (i.e., an unexpected event). The Sponsor or its designee is responsible for reporting SUSARs associated with the use of the study drug to the regulatory agencies and competent authorities after being notified of the event.

10.4 Discontinuation due to Adverse Events

Any subject who experiences an AE, serious or non-serious, may have study drug discontinued at any time at the discretion of the Investigator. The AE(s) should be noted on the appropriate eCRFs, and the subject's progress should be followed until the AE is resolved or stabilized as determined by the Investigator. The Sponsor's Medical Director and the CRO Medical Monitor must be notified. If the AE relates to overdose of study treatment, the IB should be consulted for details of any specific actions to be taken.

Subjects should return to the study to complete assessments as outlined in [Section 6](#).

10.5 Pregnancy

Pregnancies occurring in female subjects or in a male subject's partner while enrolled in this clinical study through 30 days after the last dose of study drug administration, must be reported on a Pregnancy Monitoring Form and sent to the CRO's Drug Safety Department within 24 hours of the Investigator, designee, or site personnel learning of the pregnancy (in accordance with [Section 10.3](#)).

If a subject becomes pregnant while taking study drug, the study drug will be immediately discontinued, and the pregnancy must be reported to the CRO's Drug Safety Department within 24 hours. The Investigator will discuss with the subject the risks and concerns of investigational drug exposure to a developing fetus and counsel the subject and/or pregnant partner (or ensure such counseling is provided).

All pregnancies will be followed through to a definitive outcome (i.e., birth and 3 months post-delivery, spontaneous/elective abortion or miscarriage). An uncomplicated pregnancy will not be considered an AE or SAE. Pregnancy complications (e.g., spontaneous abortion/miscarriage or congenital anomalies) are considered an SAE. The outcome of any pregnancy and the presence or absence of any congenital abnormality will be recorded in the source documentation and reported to the CRO's Drug Safety Department in accordance with [Section 10.3](#).

The Investigator will complete a Pregnancy Monitoring Form and report the information regarding the pregnancy, outcome, and status of the newborn and mother, as appropriate.

11 DATA ANALYSIS AND STATISTICAL PLANS

This section describes the statistical methodology to be used in the analysis of the protocol endpoints. Details of all planned analyses will be specified in a separate Statistical Analysis Plan (SAP).

Data will be summarized using descriptive statistics. Continuous variables will be summarized using mean, standard deviation (SD), coefficient of variation (CV%, as appropriate), median, minimum, maximum, and, as appropriate, geometric mean. Categorical variables will be summarized by presenting the number (frequency) and percentage in each category.

Data will be summarized by dose level (900 mg, 1500 mg) and overall (total subjects). All collected data will be presented in data listings.

11.1 Sample Size

The study will enroll up to approximately 32 subjects; up to approximately 16 subjects in Part A and up to approximately 16 subjects in Part B.

11.2 Analysis Populations

The following populations will be considered in the analysis of data for this study.

Efficacy Evaluable (EE) Population: All subjects who complete dosing for at least 20 days within the first 30 days of the treatment period or at least 60 days for the entire 90-day treatment period will be included in the EE Population. The EE Population will be the primary Population for all efficacy data presented.

Safety Population: All subjects who receive any amount of study drug will be included in the Safety Population. The Safety Population will be the primary population for all safety data presented.

PK Population: The PK Population will consist of all subjects who receive active study drug and have at least one measured concentration at a scheduled PK time point after start of dosing for at least one PK analyte. If any subjects are found to be noncompliant with respect to dosing or have incomplete data, protocol violations, or clinical events that affect PK, a decision will be made on a case-by-case basis as to their inclusion in the analysis. Subjects in this Population will be used for all PK summaries.

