3 INVESTIGATIONAL PLAN

3.1 Study Design

This is an open label study that will be conducted in two parts. Together, Parts A and B will provide safety and efficacy data across the two GBT440 doses that are expected to improve oxygen saturation in the enrolled subjects.

Approximately up to 32 eligible subjects will be enrolled in the study.

- In Part A (Figure 1), up to approximately 16 eligible IPF subjects will receive 900 mg of GBT440 administered orally as 3×300 mg capsules or tablets once daily for 90 days.
- In Part B (Figure 1), up to approximately 16 eligible IPF subjects will receive 1500 mg of GBT440 administered orally as 5×300 mg capsules or tablets once daily for 90 days.

Subjects enrolled in Part A will follow the GBT440 900 mg visit schedule. Subject enrolled in Part B will follow the GBT440 1500 mg visit schedule. Schedules of Assessments are provided in [Appendix A \(Table 15-1 for Part A; Table 15-2 for Part B\)](#).

A signed and dated informed consent form (ICF) must be obtained before any study-specific tests may be performed.

[figure not shown]
The screening period for each subject commences when the subject undergoes the first study-specific screening assessment and must be completed and tests evaluated before dosing (Day 1). Subjects may be rescreened up to 2 times, if deemed appropriate by the Principal Investigator. The rescreening visit should not occur sooner than 10 calendar days after the failed screening visit.

After the screening visit, the study includes the following study periods ([Figure 3-1](#)):

[figure not shown]
- Treatment period (90 days): subjects in Part A will receive 900 mg (3×300 mg) and subjects in Part B 1500 mg (5×300 mg) capsules or tablets daily
- Safety follow up (30 days): safety will be assessed for at least 5 half-lives after the last dose of GBT440 in both Parts A and B

Figure 3-1 Study Design

Part A

Part B

Subjects, who discontinue for reasons unrelated to toxicity, may be replaced if:

- the subject does not take at least 80% of their daily doses of study drug, prior to Day 30 (24 days) or Day 90 (72 days)

and/or

- the subject does not take study drug for at least 8 consecutive days prior to Days 30 or 90

The end of the study is defined as the date when the last subject last visit occurs, which is expected to be approximately 120 days after the last subject is enrolled.

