3.2 Endpoints

3.2.1 Primary Endpoint

The primary endpoint is change and % change from baseline in oxygen saturation at rest (SpO₂ or SaO₂), measured while breathing room air, at Days 30 and 90.

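### The single either/or efficacy evaluable population lets subjects long off drug count as evaluable at Day 90, and under-dosed subjects count at Day 30

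*Protocol*

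**What the plan says.** Protocol Section 11.2 sets one dosing rule for the EE population: a subject must "complete dosing for at least 20 days within the first 30 days of the treatment period or at least 60 days for the entire" span of 90 days. It adds: "The EE Population will be the primary Population for all efficacy data presented". Section 3.2.1 sets the primary endpoint as change in resting oxygen saturation, "measured while breathing room air, at Days 30 and 90". Nothing says that EE membership is judged separately at each visit.

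Section 6.3 asks subjects who stop study drug to keep attending the planned visits. Off-drug Day 90 measurements are therefore expected. On elimination, Section 3.1 says of the 30-day follow-up that "safety will be assessed for at least 5 half-lives after the last dose of GBT440".

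A different dosing standard governs replacement. Under Section 3.1 and the synopsis, subjects "who discontinue for reasons unrelated to toxicity, may be replaced if" they fall short of "at least 80% of their daily doses of study drug, prior to Day 30 (24 days) or Day 90 (72 days"), and/or if "the subject does not take study drug for at least 8 consecutive days prior to Days 30 or 90".

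Section 11.3.1 leaves the details of efficacy analysis to the SAP. The SAP covers safety only, for an abbreviated report, and defines only the Safety population (SAP Sections 2, 3 and 6). Section 11.2 is therefore the only rule on who counts in an efficacy table.

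**The concern.** An evaluable set defined by dosing would normally be read as the subjects who had enough drug for the measurement to be informative. Three features work against that reading.

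- The *or* lets the 30-day limb qualify a subject for Day 90, and the 90-day limb qualify a subject for Day 30.
- Neither limb requires dosing near the visit.
- The dosing level that makes a subject evaluable (67%) is lower than the level below which the protocol regards a subject who discontinues as replaceable (80%).

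The study has no control arm and no hypothesis test, so the EE mean change is itself the efficacy result. If it mixes on-drug and washed-out values, a reader cannot tell a weak drug effect from an effect averaged over people no longer taking the drug.

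**Working it through.** **Inputs.** EE limbs: 20 of 30 and 60 of 90 days (Protocol 11.2). Replacement limits: 24 and 72 days (3.1). Follow-up: 30 days, at least 5 half-lives (3.1). Early Termination visit: 2 weeks ±7 days, also said to give at least 5 half-lives (6.3). Size: up to about 16 per part (11.1).

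**1. The plan's own figure.** 0.80 × 30 = 24 and 0.80 × 90 = 72. The replacement limits reproduce exactly.

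**2. The EE limbs.** 20/30 = 60/90 = 66.7%. Because of the *or*, the least total dosing that qualifies is 20/90 = 22.2%.

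**3. Half-life bound.** The documents give no half-life for IPF subjects. Section 3.1 implies at most 30/5 = 6 days. The Early Termination timing in Section 6.3 implies at most 7/5 = 1.4 to 21/5 = 4.2 days. The two statements should be reconciled. The 6-day bound is the less favourable to the concern, so it is used as the main case.

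**4. Drug remaining at Day 90.** Residual = 2^(−days off / half-life).

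| Last dose | Days off | Half-lives (6 d) | Residual (6 d) | Residual (4.2 d) |
|---|---|---|---|---|
| Day 20 | 70 | 11.67 | 0.03% | 0.001% |
| Day 30 | 60 | 10 | 0.10% | 0.005% |
| Day 60 | 30 | 5 | 3.1% | 0.71% |
| Day 72 | 18 | 3 | 12.5% | 5.1% |

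These figures are for the nominal visit day. The Day 90 window is ±5 days, so a Day 60 stopper seen five days early has 25/6 = 4.17 half-lives and 2^(−4.17) = 5.6% remaining. The conclusion is the same.

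The last row shows that raising the threshold to 72 days would not by itself ensure that subjects are on drug at Day 90.

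**5. The converse at Day 30.** Sixty treatment days follow Day 30. A subject dosed on Day 1 and on 59 of those 60 days meets the 60-day limb with 1/30 = 3.3% of the dosing due before the Day 30 visit. This is the extreme case. Ten of the first 30 days plus 50 later ones also qualifies.

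**6. Who supplies a Day 90 value.** Tables 15-1 and 15-2 schedule the oxygen titration test (OTT) and arterial blood gas (ABG) at Day 90 but not at Early Termination. SpO₂ at Early Termination is taken on supplemental oxygen (footnote i). Only subjects who stop drug, stay in the study and complete the Day 90 OTT and ABG are affected.

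**7. Dilution.** Let k of n observed values come from subjects with no residual effect, and let the others share a common effect δ. The mean is then (1 − k/n)δ. With n = 16, k = 1 gives 1/16 = 6.25% and k = 2 gives 12.5%. With fewer observed values each such subject weighs more. The values of k are illustrations.

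**8. Overlap with replacement.** A subject with 20–23 dosing days by Day 30, or 60–71 by Day 90, meets the corresponding EE limb but falls below the corresponding replacement limit.

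**The case against.** **The two rules serve different purposes.** A reader might infer that Sections 3.1 and 11.2 contradict each other. They do not. Replacement is permissive, applies only to discontinuations unrelated to toxicity and governs recruitment. The EE rule governs analysis, and nothing requires equal thresholds. This objection stands, so the difference is a mismatch of standards.

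**Nobody is counted twice.** A reader might also infer that a replaced subject and the replacement fill one slot twice. They are two people with their own baselines and values, and enrolment is only up to approximately 16 per part. This stands too.

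**No on-treatment aim is stated.** The primary objective asks about the effect at Days 30 and 90 against baseline, and Section 6.3 deliberately keeps off-drug subjects under observation. It would go too far to say that the rule misestimates a declared on-treatment effect. But a set defined by dosing and called evaluable does not serve an aim of including everyone regardless of dosing either, since it still excludes those who took little drug.

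**A visit-specific reading was probably intended.** The two limbs match the two visits. That is plausible but not written, and it would still leave the Day 60 stopper evaluable at Day 90.

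**Tighter dosing rules select on adherence.** They would remove subjects who stopped early for adverse events, and in an uncontrolled study that can favour those who tolerate the drug. This is a real trade-off, and it is why the fix includes an all-dosed table.

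**Little rests on it formally.** Efficacy is descriptive and unpowered, and Section 11 promises listings of all collected data, so off-drug subjects could be identified. This limits the severity but does not correct the summary means.

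**Conclusion.** The concern holds. As written, Section 11.2 admits to the Day 90 primary summary subjects whose last dose was as early as Day 20, and to the Day 30 summary subjects with almost no dosing before it. Neither document corrects this.

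The wash-out conclusion rests on the protocol's own half-life statements and on first-order elimination, and it holds across the range they imply. The dilution of about 6% per subject rests on three assumptions: no residual effect, equal effects in all other subjects, and 16 observed values. The documents give no expected number of such subjects, so the total effect cannot be estimated.

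Dilution may also not be the whole effect. Section 6.3 lists a new IPF medication and pulmonary rehabilitation among the reasons to stop study drug. Subjects who stopped for those reasons could move the mean either way.

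Severity is should-fix. The rule decides whose values enter the primary means. However, the efficacy analysis is descriptive and unpowered, and the current SAP covers safety only.

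**What to change.** Amend Section 11.2, and carry the same text into whichever analysis plan governs any efficacy reporting, since the current SAP has no efficacy section.

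1. **Make EE visit-specific.** Use the first-30-day limb for Day 30 only and the 90-day limb for Day 90 only.
2. **Add a recency condition before each visit.** The 8-consecutive-day clause in Section 3.1 is a natural basis but must be clarified first. It can mean a gap of at least 8 days, or a failure to take drug on 8 days running before the visit.
3. **Reconcile the thresholds.** Either align the EE dosing threshold with the 80% figure (24/30 and 72/90) or state why it differs.
4. **Show the same tables for all dosed subjects** with a value at that visit, including replaced subjects, so that selection on adherence is visible.

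The half-life statements in Sections 3.1 and 6.3 should be reconciled at the same time.

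**Cost.** One paragraph of text, one extra set of descriptive tables and no new data. The EE n falls slightly at Day 90, and at Day 30 as well if the threshold is raised or the recency condition excludes anyone.
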